**Analysis Plan for:**

**Development and Pilot Trial of an Intervention to Reduce Disclosure Recipients Negative Social**

**Reactions and Victims Psychological Distress and Problem Drinking**

**NCT03488927**

**Last approved August 25, 2020**

**Contents:**

**Analysis Plan**

## Analysis Plan

**Main effects.** Treatment effect analyses compared participants in the intervention group who attended (Tx-Attender;  $n = 305$ ) to both: (a) participants who were invited to the treatment but who did not attend (Tx-Nonattender;  $n = 531$ ) and (b) participants in the control group ( $n = 432$ ). We conducted ANCOVA analyses in SPSS. We added contrasts to compare the three groups using the /LMATRIX subcommand. Covariates included gender, year in college, and alcohol use in the past 30 days, based on baseline differences in these variables. We used these covariates for all models except those models including alcohol use frequency or binge drinking as moderators, where we only included gender and year in college (because there was no variability in alcohol use in the past 30 days with these moderators).

Dependent variables differed by hypothesis. To test Hypothesis 1, we compared the three groups on T2 intended reactions, among participants who responded about intentions at T2 ( $n = 415$ ). To test Hypothesis 2, we compared the three groups on T2 actual reactions, among participants who responded about actual reactions at T2 ( $n = 474$ ). To test Hypothesis 3, we compared the T2 scores on intermediary variables of all participants, with the T1 score of each outcome as a covariate to assess for differences in change.

**Moderation analyses.** We explored four categories of moderators: demographic, IPV/SA, alcohol use, and characteristics of actual disclosures. To explore moderation, intervention condition was operationalized via two dummy codes: Tx-Attender (1) vs. Control (0) and Tx-Attender (1) vs. Tx-Nonattender (0). We then entered these dummy-coded variables into a regression model in SPSS along with covariates consistent to the covariates in the main effect analysis, main effect of the moderator, and the two interactions of interest (i.e., interaction between each dummy-coded treatment variable and moderator). For example, for gender, we

included both gender  $\times$  Control and gender  $\times$  Tx-Nonattender in the model. Each moderator was tested separately. In cases of significant interactions, we used the SAS PROCESS macro to probe the direction of the interaction by looking at the simple effect of the intervention at both levels of dichotomous moderators and at high and low values ( $\pm 1 SD$ ) of continuous moderators. We did not include moderators where the sample size of the group was five or fewer.

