Study Protocol for:

Development and Pilot Trial of an Intervention to Reduce Disclosure Recipients Negative Social

Reactions and Victims Psychological Distress and Problem Drinking

NCT03488927

Last approved August 25, 2020

Contents:

Study Protocol

Research Design

Participants were assigned to either the treatment condition or the wait-list control condition. Because a large number of participants ($n = 531$; 63.50% of participants invited) who were assigned to the treatment condition did not attend the actual intervention, we created three groups for the purposes of analyses: control ($n = 432$), treatment attender (Tx-Attender; $n = 305$), treatment non-attender (Tx-Nonattender; $n = 531$).

Procedures

The study took place at a residential, medium-size public university in the northeastern United States and received approval from the university's Institutional Review Board. The university's Dean of students sent emails to randomly selected, full-time, undergraduate students between the ages of 18 and 24 on the behalf of the researchers. These emails (initial and two reminders) were sent via mass email to 7,000 students in four batches across four weeks in the fall of 2018. We also sent an email from the research team to all professors at the University with classes greater than 60 students ($n = 205$ professors), as identified by the course catalog. Lastly, we posted fliers in residence halls and other shared spaces about the study.

Overall, 1,831 students started the baseline survey, of whom 1,268 consented to and completed the survey. Of our final 1,268 participants, 78.4% ($n = 994$) were recruited via official email from the Dean of students, 14.4% ($n = 183$) were recruited via a friend (i.e., a friend forwarded the study information), 4.9% ($n = 62$) were recruited via professors, 1.3% ($n = 16$) were recruited via fliers, 0.6% ($n = 8$) were recruited via the website, and 0.4% ($n = 5$) were recruited in another way (e.g., "Facebook"). Qualtrics randomized participants into intervention and control groups. Participants were initially randomized at a 50/50 rate to the intervention and control conditions. However, we found that rates of intervention attendance were lower than

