expected. Thus, in order to achieve desired numbers of intervention participants, when we reached over 400 in the control group, we began assigning 100% of participants who were randomly selected to be emailed to the intervention group. Because participants were recruited via professors and fliers were not randomly selected, these participants were randomized 50/50. Thus, 65.9% of participants were assigned to the intervention ($n = 836$) and 34.1% were assigned to control ($n = 432$). Participants randomized into the intervention group were invited to attend the intervention, which was conducted in two sessions (initial session and booster session). Initial session attendance was 36.2% ($n = 303$); of those, 83.1% ($n = 252$) attended the booster.

Participants first completed the baseline survey (Time 1). An average of two weeks later, those in the intervention group participated in the first intervention session. The follow-up survey (Time 2) occurred 6 months after the first intervention session, and, for control participants, 6 months and 2 weeks after their baseline survey (to ensure receipt of email at times comparable to intervention participants). We sent participants up to eight total text, email, and call reminders to remind them of the Time 2 survey. Of the 1,268 baseline participants, 70.1% ($n = 889$) completed the Time 2 survey, including 314 in the control condition and 575 in the intervention group. Participants received \$15 and \$25 gift cards for completing Time 1 and 2, respectively. Of the 305 participants who attended the first session, 252 (82.6%) attended the booster session. Participants also received reminder texts, emails, and calls to remind them about the initial and booster sessions; they received up to five of these reminders.

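### Both named treatment-effect contrasts and both moderation codes split the intervention arm by attendance, and no analysis by assigned arm is described, so selection into attendance is confounded with the effect

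*SAP*

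**What the plan says.** The Protocol (Research Design) explains that because 531 people "who were assigned to the treatment condition did not attend the actual intervention, we created three groups for the purposes of analyses": control (432), Tx-Attender (305) and Tx-Nonattender (531).

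The SAP (Analysis Plan, Main effects) then states: "Treatment effect analyses compared participants in the intervention group who attended" with (a) the non-attenders and (b) the controls. Hypotheses 1 to 3 all use the three groups. On adjustment it says: "Covariates included gender, year in college, and alcohol use in the past 30 days, based on baseline differences in these variables". The Time 1 score is added for Hypothesis 3 only. Under Moderation analyses, "intervention condition was operationalized via two dummy codes: Tx-Attender (1) vs. Control (0) and Tx-Attender (1) vs. Tx-Nonattender (0".

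Two further statements affect the remedy.

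- The Protocol (Procedures) reports that allocation began at 50/50. Once control exceeded 400, "we began assigning 100% of participants who were randomly selected to be emailed to the intervention group". Of recruits from professors and fliers it says "these participants were randomized 50/50".
- The SAP limits Hypothesis 1 to those "among participants who responded about intentions at T2" (415 people) and Hypothesis 2 to those who responded about actual reactions at Time 2 (474 people).

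**The concern.** Attendance is a decision made after assignment by a minority of those invited. The control group mixes people who would have attended with people who would not. The non-attender group contains only people who did not attend. Comparing attenders with either group therefore sets a self-selected subset against a different kind of population, and randomisation does not make the two comparable.

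The three covariates were picked because they differed at baseline. They can remove only the part of selection they measure, and they say nothing about motivation or interest in the topic. Hypotheses 1 and 2 have no stated baseline-outcome covariate.

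The plan nevertheless calls these contrasts treatment effects. If attenders would have reacted better to disclosures anyway, the pilot would credit the intervention with it. If they would have reacted worse, a real benefit could be hidden. Neither the direction nor the size can be learned from the documents.

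**Working it through.** **The plan's own counts.** 305 + 531 = 836 and 836 + 432 = 1,268. 531/836 = 63.5%, as the Protocol states. The attendance share is p = 305/836 = 36.5%. Procedures also gives initial attendance as 303 (36.2%), but 303 + 531 = 834, so only 305 fits the arm total. Time 2 completers are 575 intervention and 314 control (889).

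**Bias with no intervention effect.** Let would-be attenders differ from would-be non-attenders by d SD; the documents give no d. Under randomisation the control mean is p × (attender mean) + (1 − p) × (non-attender mean).

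- Attender vs control: (1 − p) × d = (531/836) × d = 0.635d.
- Attender vs non-attender: d.

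**Chance of a false positive.** Assumptions: two-sided 5% normal test, SD of 1, no covariate adjustment, all 889 completers used for Hypothesis 3, and groups split in proportion. SE = √(1/n₁ + 1/n₂). For Hypothesis 3 against control, √(1/210 + 1/314) = 0.089. At d = 0.2 the bias is 0.127, or 1.42 SE, and the test rejects 30% of the time.

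| Hypothesis | Attender / non-attender / control | SE vs control; vs non-attenders | d = 0.1 | d = 0.2 | d = 0.3 |
|---|---|---|---|---|---|
| 3 (889) | 210 / 365 / 314 | 0.089; 0.087 | 11% / 21% | 30% / 64% | 57% / 93% |
| 1 (415) | 98 / 170 / 147 | 0.130; 0.127 | 8% / 12% | 16% / 35% | 31% / 66% |
| 2 (474) | 112 / 195 / 167 | 0.122; 0.119 | 8% / 13% | 18% / 39% | 34% / 72% |

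Each d cell gives the rejection rate against control, then against non-attenders.

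**Is 836 vs 432 a safe substitute?** If allocation ran 50/50 apart from the switch, about 432 intervention participants have concurrent controls and 836 − 432 = 404 (48%) do not. If those late enrolees differ by h SD (assumed), the bias is (404/836) × h = 0.483h, with SE √(1/575 + 1/314) = 0.070. The unadjusted test rejects about 11%, 28% and 54% of the time at h = 0.1, 0.2 and 0.3. A simulation of 4,000 replicates gave 10%, 27% and 54%. In the same simulation, the concurrently randomised comparison (432 × 575/836 = 297 vs 314) rejected 4.5% to 5.4% of the time throughout.

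**The case against.** The strongest objection is that the Hypothesis 3 rates describe an unadjusted analysis, while the SAP adjusts for the Time 1 score. Suppose the gap is the same at both times and the two scores correlate at r (assumed). Adjustment multiplies the bias by (1 − r) and the SD by √(1 − r²), so bias over SE shrinks by √((1 − r)/(1 + r)). At r = 0.6 that factor is 0.5, and the d = 0.2 rates fall from 30% / 64% to 11% / 21%, the same as the d = 0.1 column. At r = 0.8 they fall to 8% / 12%. This stands: the Hypothesis 3 figures are best read against the gap that remains after adjustment. It does not help Hypotheses 1 and 2, and it does not remove unmeasured selection.

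Second, drift between early and late enrolees is speculative. Emails went to randomly selected students in four batches over four weeks, and at h = 0.05 the full comparison rejects only 6.4% of the time. That is fair as to size. But late emailed participants have no concurrent controls, so once period and source are adjusted for they add almost nothing to the arm contrast. Restricting the primary set therefore loses little.

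Third, an assigned-arm analysis is not fully protected either. Time 2 completion was 314/432 = 72.7% in control and 575/836 = 68.8% in intervention, and the Hypothesis 1 and 2 sets are defined by Time 2 response. These limits remain.

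Finally, this is a pilot, its moderation is exploratory and its groups are openly labelled by attendance. The instruction to contrast all three groups may also cover non-attender vs control. These points lower the urgency, but that third contrast still splits the arm by attendance, and no comparison of whole arms is named.

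**Conclusion.** The concern holds and must be fixed. Neither named treatment-effect contrast, and neither moderation code, compares groups formed by assignment alone, and the documents offer no assigned-arm or complier analysis beside them.

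That conclusion rests on the text and needs no assumption. The size does: it depends on a selection gap that the documents do not report. Even a remaining gap of 0.1 SD would roughly double the nominal 5% error against control for Hypothesis 3 and quadruple it against non-attenders. Using 303 rather than 305 attenders changes none of this, though the two counts need reconciling because attendance is the exposure in any complier analysis.

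**What to change.** 1. **Primary analysis.** For each hypothesis, run an ANCOVA by assigned arm regardless of attendance, in that hypothesis's own Time 2 set. Restrict it to people enrolled while their recruitment source was allocated 50/50: emailed participants before the switch, and professor and flier recruits throughout. Adjust for allocation period and recruitment source as well as the planned covariates.
2. **Unclear sources.** State from the Qualtrics log how friend, website and other recruits (183 + 8 + 5 = 196) were allocated after the switch. Include them only while their allocation was 50/50.
3. **Sensitivity analysis.** Report the full 836 vs 432 comparison with the same adjustment, labelled as not purely randomised.
4. **Effect of attending.** Estimate a complier average causal effect by two-stage least squares in the concurrently randomised set, with the same covariates. State the assumptions that assignment acts only through attendance and that no control attended.
5. **Moderation.** Test assigned arm × moderator in that set.
6. **Labels.** Call the two attender contrasts non-randomised and descriptive.
7. **Hypotheses 1 and 2.** The two sets appear complementary (415 + 474 = 889). Report membership by assigned arm, and caveat the results if it differs.

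**Cost.** SAP wording and a re-run using enrolment date and recruitment source; no new data. The price is precision. The table gives the difference detectable with 80% power (2.80 × SE, unadjusted), with the equivalent effect among attenders (divided by 0.365) in brackets. The size of the concurrent set is not given, so 432 intervention participants are assumed, with a range of 432 ± 1.96 × √864, or 374 to 490.

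| Hypothesis | All Time 2 completers | Concurrent set | Concurrent set over the 374–490 range |
|---|---|---|---|
| 3 | 0.20 SD (0.54) | 0.23 SD (0.62) | 0.22–0.24 SD |
| 1 | 0.29 SD (0.79) | 0.33 SD (0.91) | 0.32–0.34 SD |
| 2 | 0.27 SD (0.74) | 0.31 SD (0.85) | 0.30–0.32 SD |

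Such imprecision is acceptable in a pilot if it is reported.

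### The H1 and H2 attender contrasts do not use the T1 intermediary scores that H3 uses, so measured confounding by those scores may remain; adding them is a cheap sensitivity analysis

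*SAP*

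**What the plan says.** The Protocol (Research Design) explains that because many of those assigned to treatment "did not attend the actual intervention, we created three groups for the purposes of analyses": 432 controls, 305 attenders and 531 non-attenders. Under Procedures it reports that "65.9% of participants were assigned to the intervention" (836 of 1,268). That share followed a change of allocation: once there were more than 400 controls, all further randomly emailed participants went to the intervention, while those reached through professors or fliers stayed at 50/50.

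In the SAP (Analysis Plan, Main effects), the covariate rule is: "Covariates included gender, year in college, and alcohol use in the past 30 days, based on baseline differences in these variables". It covers all models "except those models including alcohol use frequency or binge drinking as moderators, where we only included gender and year in college".

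The three hypotheses are then treated as follows.
- H1 (n = 415): "To test Hypothesis 1, we compared the three groups on T2 intended reactions, among participants who responded about intentions at T2". No T1 score is named.
- H2 (n = 474): "To test Hypothesis 2, we compared the three groups on T2 actual reactions, among participants who responded about actual reactions at T2". No T1 score is named.
- H3: "we compared the T2 scores on intermediary variables of all participants, with the T1 score of each outcome as a covariate".

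The moderation models enter the treatment and moderator terms "along with covariates consistent to the covariates in the main effect analysis", so they add no T1 scores either. The SAP does not list the variables that were screened for baseline differences. Neither document says whether intended or actual reactions were measured at T1.

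**The concern.** Attenders are the 36.5% of those invited (305/836) who chose to come. Neither the contrast with non-attenders nor the contrast with controls is protected by randomisation, so covariate adjustment carries most of the burden against selection. The SAP itself reports that the groups differed at baseline on the three covariates it chose.

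If attenders also differed at T1 on intermediary scores that predict reactions, and the three covariates do not absorb the difference, that part would appear in H1 and H2 as a treatment effect. Its direction is unknown. The Protocol places the T1 survey about two weeks before the first session, so these are pre-treatment values. Adjusting for them does not adjust away an effect of the intervention.

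**Working it through.** **1. Counts.** 305 + 531 = 836; 836 + 432 = 1,268; 314 + 575 = 889 T2 completers; 415 + 474 = 889. The counts agree. The last sum suggests, without proving it, that each T2 completer answered one of the two reaction item sets. The Protocol also gives 303 for first-session attendance; 305 is used here because both documents use it for the analysis groups.

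**2. Assumed group sizes.** T2 numbers by attendance are not given. With equal retention among those invited, attenders are 575 × 305/836 = 210 and non-attenders 365; controls are 314. Multiplying by 415/889 gives H1 sizes of 98, 170 and 147. Multiplying by 474/889 gives H2 sizes of 112, 195 and 167 (attenders, non-attenders, controls).

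**3. Bias.** In outcome SD, bias = R × d. Here d is the group gap on the fitted composite of the added scores that remains after the current covariates, and R is the multiple partial correlation of those scores with the outcome. The documents give neither. Assuming d = 0.2 and R = 0.1 to 0.3: 0.1 × 0.2 = 0.02 and 0.3 × 0.2 = 0.06.

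**4. True error.** SE = √(1/n₁ + 1/n₂), and error = Φ(−1.96 + bias/SE) + Φ(−1.96 − bias/SE). The documents state no alpha; two-sided 5% is assumed.

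| Contrast | SE | Error, bias 0.02 | Error, bias 0.06 |
|---|---|---|---|
| H1 attender vs control | 0.130 | 5.3% | 7.5% |
| H1 attender vs non-attender | 0.127 | 5.3% | 7.6% |
| H2 attender vs control | 0.122 | 5.3% | 7.8% |
| H2 attender vs non-attender | 0.119 | 5.3% | 8.0% |

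**5. Sensitivity.**
- d = 0.1, R = 0.1 to 0.3: bias 0.01 to 0.03, error 5.1 to 5.7%.
- d = 0.4, R = 0.3: bias 0.12, error 15 to 17%.
- All 305 attenders answering T2: H2 attender vs control becomes 163 vs 167, SE 0.110, and the upper figure becomes 8.5%.
- Simulation of the H1 attender vs non-attender contrast with one T1 score (4,000 runs per setting; gaps 0 to 0.3, correlations 0.2 to 0.6): adding the score brought bias to about 0 and error to about 5%. SE fell from 0.127 to 0.116 at correlation 0.4.

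**6. Could a baseline screen have settled it?** Assume pairwise 5% tests on the full baseline sample and attenders differing equally from both other groups.
- Against 432 controls: SE = √(1/305 + 1/432) = 0.0748.
- Against 531 non-attenders: SE = √(1/305 + 1/531) = 0.0718.
- The tests share the attender mean, so their correlation is (1/305)/(0.0748 × 0.0718) = 0.61.
- At 0.2 SD, z = 2.67 and 2.78. Taken singly the tests miss 24% and 20% of the time; both miss about 11% of the time.
- At 0.1 SD, singly 73% and 71 to 72%; both miss about 60% of the time.

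**7. Cost in precision if the scores explain nothing.** The number of scores k is not stated. Taking 6 parameters in the current model, the SE multiplier is √(df/(df − k)). H1, df = 409: 1.004, 1.006 and 1.012 for k = 3, 5 and 10. H2, df = 468: 1.003, 1.005 and 1.011. A 0.2 SD composite gap (98 vs 147) also gives r² = 0.04/(0.04 + 1/0.24) = 0.0095, which multiplies the SE by 1.005.

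**The case against.** The strongest reply is that nothing has been shown to be wrong. The documents report no T1 imbalance and no correlation, and the error figures follow the assumed inputs: correlations up to 0.6 with a 0.3 SD gap would give about 29% for the H1 attender vs non-attender contrast. That stands. A reader might infer that the H1 and H2 results are biased, or that their error rate is 15% or more. The documents support neither.

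A second reply is that covariates were chosen from baseline differences, so the T1 scores may have been screened and found balanced. A screen would also miss a gap less often than either test alone suggests: about 11% at 0.2 SD, and less than 0.04% at 0.4 SD. This also stands in part. But the SAP does not say that these scores were screened, a 0.1 SD gap would usually pass, and a screen of the full baseline sample would not establish balance among the 415 and 474 who answered at T2.

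Three further readings go beyond the text.
- It is tempting to call the intermediary variables attitudes. The SAP never names them or shows that they predict reactions.
- It is tempting to say that T1 scores are complete for everyone. In the H3 sentence, the reference to all participants attaches to the T2 scores, and T1 completeness is not reported.
- It is tempting to ask for the moderation models to be re-run. The SAP calls those exploratory, and no figure here bears on an interaction term.

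Finally, the larger weakness is comparing by attendance at all, and extra covariates could lend such a contrast credit it has not earned. That is right, and it limits what this point can claim.

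**Conclusion.** The point holds as a low-severity improvement. H1 and H2 adjust for three covariates in contrasts built on self-selection. They leave out pre-treatment scores that H3 shows were collected, and nothing in the plan establishes balance on those scores among the T2 respondents. The illustrative size is modest: 5.3 to 8.0% true error at a nominal 5%. This rests on an assumed 0.2 SD residual gap, a partial correlation of 0.1 to 0.3, equal T2 retention of attenders and non-attenders, and a two-sided 5% test. It becomes large only if both the gap and the correlation are large. The actual bias cannot be computed from the documents and may be zero.

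**What to change.** Keep the current models. Beside them:
- Report H1 and H2 main-effect ANCOVAs that add the T1 intermediary scores used in H3 as one fixed set, so that scores are not picked by their results. Add T1 reaction scores if they were collected. Label this a post hoc sensitivity analysis.
- Report the size of the group difference on each T1 score.
- State as limitations that unmeasured selection by attendance and by T2 item set remains; that control versus attender is also tied to enrolment period and recruitment route, because allocation changed once controls passed 400; and that this adjustment does not replace a comparison by assigned group.

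Moderation re-runs are not required.

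The cost is SAP wording, one baseline table and a re-run, with no new data. If the scores explain nothing, the SE rises by 0.3 to 1.2% for 3 to 10 scores, plus about 0.5% if the groups differ by 0.2 SD on the composite. If the scores predict the outcome, the SE may fall. Respondents with missing T1 items need a stated rule.

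### Hypotheses 1 and 2 are presented as treatment effects but tested in subsets fixed at Time 2, with no membership comparison and no limit on interpretation

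*SAP*

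**What the plan says.** The Main effects paragraph of the SAP's Analysis Plan opens with "Treatment effect analyses compared participants in the intervention group who attended", against invited non-attenders and against controls. For Hypothesis 1 it says "we compared the three groups on T2 intended reactions, among participants who responded about intentions at T2" (n = 415), and for Hypothesis 2 "we compared the three groups on T2 actual reactions, among participants who responded about actual reactions at T2" (n = 474). Hypothesis 3, by contrast, is described for all participants with the Time 1 score as a covariate; no Time 1 outcome covariate is stated for Hypotheses 1 and 2. The models adjust for gender, year in college and recent alcohol use, chosen because they differed at baseline.

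Under Procedures, the Protocol places Time 2 six months after the first session (six months and two weeks after baseline for controls). It reports that 889 of 1,268 participants "completed the Time 2 survey, including 314 in the control condition and 575 in the intervention group". Under Research Design it explains that, because many invited participants did not attend, "we created three groups for the purposes of analyses". Procedures adds that once the control group passed 400, "we began assigning 100% of participants who were randomly selected to be emailed to the intervention group".

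The SAP's Moderation analyses paragraph lists the moderator categories as "demographic, IPV/SA, alcohol use, and characteristics of actual disclosures".

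**The concern.** Each analysis set is defined by an answer given at Time 2, so assignment or attendance could have influenced who is in it. If membership differs between groups and is related to the outcome, part of a Hypothesis 1 or 2 difference would reflect who entered the set and not how people changed. Interactions with characteristics of actual disclosures appear to rest on the same kind of post-assignment event.

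The documents give no rule for who answered which item set, no membership by arm or group, no baseline balance within the sets and no sensitivity analysis for selection. The three covariates were chosen for baseline differences, not as predictors of entry to a set. Following the plan exactly therefore labels contrasts within about a third of the assigned participants as treatment effects. The problem adds to the non-comparability already created by splitting the invited arm on attendance and by changing the allocation during recruitment.

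**Working it through.** **Counts.** 415 + 474 = 889 = 314 + 575, which reproduces the Time 2 total in the Protocol; 889/1,268 = 70.1%, as stated. Shares of those assigned: 415/1,268 = 32.7% and 474/1,268 = 37.4%. Shares of completers: 46.7% and 53.3%. The exact sum suggests that each completer was routed to one set; the documents do not say so.

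**Completion by arm.** Control 314/432 = 72.7%; intervention 575/836 = 68.8%. The difference is 3.9 points, with a 95% half-width of 1.96 × √[0.701 × 0.299 × (1/432 + 1/836)] = 5.3 points.

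**Estimated 50/50 sample.** The 100% rule sent people only to the intervention, so all 432 controls came from 50/50 randomisation. The number of invited participants randomised alongside them is then roughly negative binomial(432, 0.5): mean 432, 95% range 376 to 491. Assuming the 68.8% completion rate also applies to them, there are 432 × 575/836 = 297 intervention completers and 314 control completers, 611 in all.

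**What a membership test could show.** The 95% half-width for the arm difference in membership among these completers is 1.96 × √[0.533 × 0.467 × (1/314 + 1/297)] = 7.9 points (8.2 with 376 invited, 7.7 with 491). A non-significant result could not exclude a 5-point difference.

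**Illustrative trimming shift.** No arm split of either set is given, so membership differences are assumed. Let m be membership among completers, with the two arms averaging to the pooled rate (weights 314 and 297). Selection is s = completion × m, the trimmed share is q = 1 − (lower s / higher s), and, for a normal outcome under monotone selection, the shift in the trimmed arm's mean is φ(z_q)/(1 − q) SD.

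Example: Hypothesis 2, intervention membership 5 points lower.
- m: control 0.5332 + 0.05 × 297/611 = 0.5575; intervention 0.5075.
- s: control 0.7269 × 0.5575 = 0.4052; intervention 0.6878 × 0.5075 = 0.3491.
- q = 0.139, z_q = −1.087, φ = 0.221, shift = 0.221/0.861 = 0.26 SD.

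| Assumed membership, intervention minus control | Hypothesis 2: q, shift | Hypothesis 1: q, shift |
|---|---|---|
| 0 (equal routing) | 0.054, 0.12 SD | 0.054, 0.12 SD |
| +3 points | 0.001, 0.003 SD | 0.009, 0.02 SD |
| −3 points | 0.106, 0.20 SD | 0.113, 0.22 SD |
| +5 points | 0.038, 0.09 SD | 0.051, 0.11 SD |
| −5 points | 0.139, 0.26 SD | 0.150, 0.27 SD |

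Direction matters because completion is already lower in the intervention arm. If the two sets do partition the completers, a higher rate in one is a lower rate in the other, so +5 points for Hypothesis 2 goes with −5 for Hypothesis 1.

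**Milder selection, membership only.** With latent correlation r between entry and outcome, the shift is r × [φ(z_mC)/mC − φ(z_mI)/mI], where mC and mI are control and intervention membership. For r = 0.3 to 0.5 at 5 points this is 0.023 to 0.039 SD (Hypothesis 2) and 0.025 to 0.041 SD (Hypothesis 1).

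**Scale.** The unadjusted 95% half-width of the arm contrast in this sample is about 0.22 SD for Hypothesis 2, from 1.96 × √(1/167 + 1/158), and 0.23 SD for Hypothesis 1, from 1.96 × √(1/147 + 1/139).

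**Planned contrasts.** These figures do not carry over to attenders. The number of attenders who completed Time 2 is not given; it lies between 575 − 531 = 44 and 305.

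**The case against.** The strongest reply has four parts.

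First, the SAP hides nothing: it names each set and gives its size. If actual reactions can be reported only by someone who received a disclosure, restriction is unavoidable for Hypothesis 2. This stands, and the criticism is limited to the missing membership comparison and the missing limit on interpretation.

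Second, the bias may be small. No difference in membership is shown, the milder model gives 0.02 to 0.04 SD, and the 3.9-point completion gap is smaller than its own half-width and includes invited participants who were not randomised 50/50. This also stands. A reader might take 0.26 or 0.27 SD as an estimate of bias; it is a worst case under an assumed difference.

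Third, trimming bounds fit this trial poorly. They compare assigned arms, while the plan compares attenders with others. Monotone selection on completion plus membership is doubtful if the two move in opposite directions; the net trimmed share can then be near zero (0.001 in one row above) although selection acts at both steps. Isolating the 50/50 participants also needs study records: the Protocol says "Because participants were recruited via professors and fliers were not randomly selected, these participants were randomized 50/50" but gives no rule after the switch for the 183 recruited through friends or for website and other recruits. The bounds are therefore optional.

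Fourth, the attendance split is the larger problem. It may be, but restoring an assigned-arm comparison would leave selection into each set unexamined.

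**Conclusion.** The concern holds in a limited form. Hypotheses 1 and 2 are called treatment effects but are contrasts within sets fixed after assignment, and neither document examines entry to those sets or narrows the conclusion. The criticism rests only on the SAP's own definition of each set, not on any inferred routing.

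Two stronger readings are tempting. A reader might infer that the intervention changed who received disclosures and so biased the results; the documents give neither the routing rule nor membership by arm or group. A reader might also infer that equal membership rates would clear the contrasts. A non-significant test leaves differences of about 8 points open, and even exactly equal rates would not make attendance-defined groups comparable.

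The illustrative range runs from about 0.003 to 0.27 SD for the worst case with differences up to 5 points. It assumes monotone selection, a normal outcome, the reported completion rates applied to the 50/50 sample, and membership differences that the documents do not give.

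**What to change.** 1. State the routing rule. Analyse membership of each set among completers, and Time 2 completion plus membership, as outcomes by assigned arm with confidence intervals. Describe both for the three groups, and tabulate baseline balance within each set. Do not read a non-significant difference as absence of selection.
2. Report the Hypothesis 1 and 2 contrasts, and interactions with disclosure characteristics, as conditional on a post-assignment event and not as treatment effects in all assigned participants.
3. Optionally, add trimming bounds by assigned arm among participants whom study records show were randomised 50/50, with selection defined as completion plus membership. State that monotonicity is doubtful if the two components move in opposite directions, and that the bounds do not correct the attender contrasts.

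The cost is some further analysis of data already held, revised wording and a narrower conclusion. The optional bounds would use a smaller sample, about 611 of the 889 completers under the assumptions above, and would give wider intervals. It is a cheap improvement.
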